8.1.1.2 Change in log-transformed seizure frequency from Baseline

The 28-day adjusted seizure frequency value will be log-transformed using the function $\ln(x+1)$, where \ln represents the natural logarithm function. The change in the log-transformed seizure frequency from Baseline is calculated as: $\ln(SFT+1) - \ln(SFB+1)$, where SFT corresponds to

the seizure frequency during an analysis period and SFB corresponds to the Baseline period seizure frequency.

For the primary efficacy variable for the FDA, SFT and SFB are the observable focal-onset seizure frequency during the 12-week Maintenance Period and Baseline Period, respectively. Only subjects with > 0 seizure frequency at baseline will be included in the summary analysis.

8.1.1.3 Percent reduction in seizure frequency from Baseline

The percent reduction in seizure frequency (PRD) from the Baseline is defined as: $PRD = [(SFB - SFT) / SFB] \times 100$, where SFT corresponds to the 28-day adjusted seizure frequency during an analysis period and SFB corresponds to the Baseline seizure frequency. A negative PRD indicates an increase in seizure frequency from Baseline.

Only subjects with > 0 seizure frequency at baseline will be included in all percent reduction analysis.

8.1.1.4 75% Responder

Responder status (yes or no) for a subject is determined by the percent reduction in seizure frequency (PRD) from Baseline. A subject is defined as a 75% responder if s/he has a reduction in seizure frequency (PRD) of at least 75% from the Baseline. The 75% responder rate (RR) will be calculated as the proportion of 75% responders. For the primary efficacy variable for the EMA, 75% responder status is calculated based on the percent reduction (PRD) from the Baseline in observable focal-onset seizure frequency during the 12-week Maintenance Period.

Only subjects with > 0 seizure frequency at baseline will be included in the analysis.

8.1.2 Analysis of the primary efficacy variables

8.1.2.1 Primary variable for submission to the US FDA, PMDA and other regulatory authorities not referencing EMA

The primary efficacy variable for the US FDA/PMDA is the change in log-transformed observable focal onset seizure frequency from Baseline, over the 12-week Maintenance Period. Analyses of the primary variable for the FDA will be performed on the FAS as described below.

Change from Baseline in observable focal-onset seizure frequency (using the log-transformed data) will be analyzed for the FAS using analysis of covariance (ANCOVA) with treatment group (PSL 400mg bid, 200mg bid, 100mg bid, and placebo) as the main factor, Baseline log-transformed seizure frequency as a continuous covariate, Baseline SV2A use (Yes or No), and Region (Europe or non-Europe) as factors. Pairwise contrasts will be constructed to compute estimated effects of each dose from placebo.

Treatment effects will be characterized using treatment differences based on back-transformation of least squares (LS) means obtained from the above ANCOVA model. Percent reduction over placebo will be calculated as $100 \times (1 - \exp(\text{diff}))$, where diff is the model estimate of the log difference between each PSL group and placebo group. Similarly, estimates for the upper and lower bounds of the 95% confidence interval (CI) will be back-transformed for table presentation as $\exp(\text{lower})$ and $\exp(\text{upper})$, respectively, where upper and lower correspond to the 95% CI of

the log difference. If there are issues with convergence, covariates will be dropped sequentially in the order of Region, and then Baseline SV2A use (Yes or No) if further needed.

Pairwise comparisons of the 400mg bid, 200mg bid, and 100mg bid PSL dose groups versus placebo will be carried out using the analysis model described above. Type 1 error will be controlled using the Hochberg step-up procedure (Section 4.5) within SAS® Proc Multtest. Both multiplicity-adjusted and unadjusted p-values will be presented.

8.1.2.2 Supportive and sensitivity analyses for the primary variable for submission to the US FDA, PMDA, Chinese FDA and other regulatory authorities not referencing EMA

Due to early termination of the study and COVID-19 global pandemic, all sensitivity analyses will not be executed.

8.1.2.3 Primary variable for submission to the EMA and regulatory authorities who reference EMA

The primary efficacy available for the EMA is the 75% responder rate over the 12-week Maintenance Period. Analyses of the primary variable for the EMA submission will be done on the FAS as described below.

The analysis of 75% responder rate will be based on a logistic regression model with factors for treatment group (PSL 400mg bid, 200mg bid, 100mg bid and placebo), Region (Europe or Non-Europe), Baseline SV2A use (Yes or No) and log-transformed Baseline seizure frequency as a continuous covariate. If there are issues with convergence, covariates will be dropped sequentially in the order of Region, and then Baseline SV2A use (Yes or No) if further needed. Odds Ratios of PSL dose to placebo will be obtained and tested for difference from unity (2-sided) for the dose groups 400mg bid, 200mg bid, and 100mg bid. The evaluation of statistical significance will be based on the Hochberg procedure as described in Section 4.5. Both multiplicity adjusted p-values and unadjusted p-value will be presented.

If there is <2 responders in a treatment group, results will also be provided for an exact conditional logistic regression model where treatment group is included in the model and Region (Europe or non-Europe) and Baseline SV2A use (Yes or No) are included as strata.

8.1.2.4 Supportive and sensitivity analyses for the primary variable for submission to the EMA and regulatory authorities who reference EMA

Due to early termination of the study and COVID-19 global pandemic, all sensitivity analyses will not be executed.

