2.6 Determination of sample size

In the event that 2 data analyses are conducted to accommodate an extended enrollment period in China, the initial data cut and analysis will be performed after all randomized non-Chinese subjects (approximately 400) have completed or terminated the study. The safety and efficacy analyses from this first data cut will serve as the basis for the European, North American, and Japanese submissions for marketing authorization. The power for this analysis is greater than 90%, at the 2-sided 5% significance level. Because of uncertainty regarding the time point when China will join the global program and the duration of recruitment in China, a second efficacy and safety analysis for all randomized subjects will also be performed: the power in this case remains greater than 90%, at the 2-sided 5% significance level. The safety and efficacy analyses from the second data cut will serve as the basis for submission for marketing authorization only for China.

The sample size was calculated based on achieving 90% power to observe a statistically significant result for either the 400mg bid and 200mg bid or 200mg bid and 100mg bid doses when compared to PBO for both the primary variable for FDA/PMDA/CFDA, change from Baseline of the log transformed ($\ln x+1$) 28-day adjusted seizure frequency, and the primary variable for EMA, the 75% responder rate. The log reduction from Baseline in seizure frequency was assumed to be 0.195 for PBO and 0.670, 0.754, and 0.780 for 100mg bid, 200mg bid, and 400mg bid doses of PSL, respectively. A common SD of 0.985 was assumed. For the 75% responder rate endpoint, assumptions were a 0.121 responder rate for PBO and corresponding responder rates of 0.301, 0.332, and 0.342 for the 100mg bid, 200mg bid, and 400mg bid doses of PSL, respectively. These estimates are based on prior experience in epilepsy together with the EP0069 study results. A significance level of 0.05 was chosen, and a 2-sided test assumed. With power of greater than 90%, a 2-sided Type-1 error of 5%, and all dose groups of the same size, 100 subjects are required per arm, giving a total of 400 subjects.

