3 DATA ANALYSIS CONSIDERATIONS

3.1 General presentation of summaries and analyses

Statistical analysis and generation of tables, figures, subject data listings, and statistical output will be performed using SAS Version 9.3 or higher. All tables and listings will use Courier New font size 9.

Descriptive statistics will be displayed to provide an overview of the study results. For categorical variables, the number and percentage of subjects in each category will be presented. Unless otherwise noted, all percentages will be displayed to 1 decimal place. No percentage will be displayed for zero counts, and no decimal will be presented when the percentage is 100%. For continuous variables, descriptive statistics will include number of subjects with available measurements (n), mean, SD, median, minimum, and maximum.

Decimal places for descriptive statistics will always apply the following rules:

- “n” will be an integer

- Mean, SD, and median will use one additional decimal place compared to the original data
- Minimum and maximum will have the same number of decimal places as the original value.

Unless otherwise specified, statistical tests of efficacy variables will be presented as two-sided p values rounded to three decimal places. P-values less than 0.001 will be presented as “<0.001” and p-values greater than 0.999 will be presented as “>0.999.” Statistical comparisons will be two-sided and will be performed at the 0.05 level of significance.

A complete set of data listings containing all documented data as well as calculated data (e.g., change from Baseline), as applicable, will be generated.

Treatment groups will be displayed as: Placebo, PSL 100mg bid, PSL 200mg bid, and PSL 400mg bid.

Log-transformation is based on natural logarithm. For analyses on log-transformed values, model estimates will be back-transformed to anti-log space for table presentation. See Section 8.1.1 for details.

Data collected at scheduled visits will be included in the by-visit summary. Data collected at unscheduled visits will not be included in the by-visit summary, but will be considered when determining the Last Visit, minimum, and maximum post-Baseline values during the Treatment Period. Data collected on Visit 8 will be summarized separately for subjects in the Conversion Period versus the Taper and Safety FU Period.

In general, all CRF data will be presented in the subject listings.

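### SAP 8.1.2.1 reports the primary effect as a percent reduction but gives its 95% confidence bounds as bare ratios in reversed order, so the stated interval cannot contain the estimate

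*SAP*

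**What the plan says.** SAP 8.1.2.1 fits an ANCOVA to the change in ln(seizure frequency + 1) and contrasts each dose with placebo. It turns the contrast into a percent reduction over placebo, 100 × (1 − exp(diff)), "where diff is the model estimate of the log difference between each PSL group and placebo group".

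The next sentence opens with *Similarly* and deals with the interval: "estimates for the upper and lower bounds of the 95% confidence interval (CI) will be back-transformed for table presentation as". Two formulas come next, first exp(lower) and then exp(upper), matched to the two bounds by the word *respectively*. Its closing clause defines the terms as limits on the log scale: "where upper and lower correspond to the 95% CI of" the log difference. Taken in order, the upper bound becomes exp(lower) and the lower bound becomes exp(upper), with no 100 × (1 − …) around either.

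The only general rule is in SAP 3.1: "For analyses on log-transformed values, model estimates will be back-transformed to anti-log space for table presentation". It refers the reader to Section 8.1.1, which defines seizure frequency, the log change, percent reduction and responder status but gives no formula for confidence bounds. The list of changes in SAP 15.1 does not touch the sentence.

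**The concern.** The estimate and its bounds are on different scales, and the bounds are inverted for the scale they are on. The formula fits neither a percent-reduction table nor a ratio table. The reversed order suggests why: 1 − exp(·) is a decreasing function, so the upper limit of a percent reduction does come from the lower limit of the log difference. The order was written for percent reductions and the conversion itself was dropped.

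This is the effect size and interval for the FDA/PMDA primary endpoint. SAP 8.2.2.1 reuses the variable as the key secondary for the EMA. SAP 8.1.2.5 repeats the model in subgroups, where SAP 4.8 rules out testing, so the estimates and intervals are the whole result. SAP 16 repeats all tables for Japan and non-Japan. With the sensitivity analyses withdrawn (SAP 8.1.2.2), this interval is the main statement of precision for the primary effect. A programmer who follows the text produces an unusable interval; one who corrects it silently departs from the approved SAP.

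**Working it through.** **Inputs (SAP 2.6).** Log reductions from Baseline are "assumed to be 0.195 for PBO and 0.670, 0.754, and 0.780 for 100mg bid, 200mg bid, and 400mg bid doses of PSL", in that order. For the spread, the plan says "A common SD of 0.985 was assumed". The plan has 100 subjects per arm and a two-sided 5% level.

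**The plan's own figure.** The documents contain no worked confidence interval. The stated figure that uses these inputs is power above 90% with 100 per arm, and it reproduces. For the log endpoint, pairwise power at 0.05 is 92.7%, 98.0% and 98.7% for 100, 200 and 400mg bid. Simulating Hochberg with a shared placebo arm gives 96.8% for the plan's criterion (400 and 200mg, or 200 and 100mg). The 75% responder endpoint gives 92.9% on the same criterion. The inputs are therefore a fair basis for illustration.

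**Interval on the log scale.**
- Differences, padsevonil minus placebo on the change scale: −(0.670 − 0.195) = −0.475; −(0.754 − 0.195) = −0.559; −(0.780 − 0.195) = −0.585.
- SE = 0.985 × √(2/100) = 0.1393.
- Half-width = 1.96 × 0.1393 = 0.273.
- 95% limits: −0.748 to −0.202; −0.832 to −0.286; −0.858 to −0.312.

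**Stated rule and consistent rule applied to the same limits.**

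| Dose | Estimate, 100 × (1 − exp(diff)) | As written: lower = exp(upper) | As written: upper = exp(lower) | Consistent: 100 × (1 − exp(upper)) to 100 × (1 − exp(lower)) |
|---|---|---|---|---|
| 100mg bid | 37.8% | 0.817 | 0.473 | 18.3% to 52.7% |
| 200mg bid | 42.8% | 0.751 | 0.435 | 24.9% to 56.5% |
| 400mg bid | 44.3% | 0.732 | 0.424 | 26.8% to 57.6% |

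As written, each lower bound exceeds its upper bound, so no value can lie between them. On the consistent rule, each interval contains its estimate.

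**If the bounds are re-sorted.** The ratio interval then contains the percent figure only when the reduction is about 0.76% to 1.30% (100 per arm), which is practically no effect.

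**If the sorted ratios are read as percentages.** The intervals become 47.3 to 81.7, 43.5 to 75.1 and 42.4 to 73.2. The first two exclude their estimates (37.8 and 42.8). The third contains 44.3, so it looks credible while overstating the correct 26.8 to 57.6.

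**Dependence on sample size.** The study ended early and the achieved numbers are not given. Assuming 25 per arm, 100mg bid still gives an estimate of 37.8, with lower bound 1.074 and upper bound 0.360; the consistent interval is −7.4% to 64.0%. At an assumed 50 per arm the values are 0.915 and 0.423, against 8.5% to 57.7%. The mismatch is in the formula and does not depend on N.

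**The case against.** The strongest counter-reading is that a ratio table was intended: exp(diff) with exp(lower) and exp(upper), and the percent reduction shown as a derived extra. SAP 3.1 speaks only of anti-log space, and the CI sentence never says outright that the interval belongs to the percent reduction. Once sorted, that ratio interval is valid and contains exp(diff), for example 0.622 (0.473 to 0.817) for 100mg bid. The reading does not rescue the text. SAP 8.1.2.1 does not specify exp(diff) as a reported estimate, *Similarly* ties the bounds to the percent-reduction formula, and the order given would still be wrong for a ratio.

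Several points on the other side do stand:
- The missing conversion and the reversed order are one slip, not two. Restoring 100 × (1 − …) makes the order correct.
- The exclusion of the estimate is absolute only for the literal, unsorted interval. After sorting it holds for any reduction of practical size.
- The ANCOVA contrasts, both sets of p-values and the Hochberg decisions do not use these bounds. Either scale can be recovered exactly from the other.
- The literal output is visibly odd, so it would probably be noticed.
- With ln(x + 1), the quantity is strictly a reduction in (frequency + 1). This applies to the SAP's own estimate as much as to the corrected bounds.

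**Conclusion.** The concern holds. SAP 8.1.2.1 states a wrong rule for the confidence interval of the FDA/PMDA primary effect, and nothing elsewhere in the SAP corrects it. At the planning values, a 37.8% reduction would be printed with bounds 0.817 and 0.473 in place of 18.3% to 52.7%, and the other two doses show the same fault.

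The figures assume 100 per arm, the unadjusted planning SD and a normal approximation. They illustrate the fault and do not predict the interval the study would report, because the ANCOVA adjusts for baseline frequency, SV2A use and region, and the achieved numbers are unknown. The fault itself rests on none of these assumptions. It affects the reported interval, not the significance tests. It should still be corrected before the tables are produced, because it is the prespecified formula for the primary result.

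**What to change.** In SAP 8.1.2.1, state that, with lower and upper the 95% limits of the log difference:
- lower limit of the percent reduction = 100 × (1 − exp(upper));
- upper limit of the percent reduction = 100 × (1 − exp(lower)).

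Apply the same rule wherever this ANCOVA is reused: the EMA secondary analysis (8.2.2.1), the subgroups (8.1.2.5) and the Japan/non-Japan tables (16). Reporting the ratio exp(diff) with exp(lower) as its lower limit and exp(upper) as its upper limit would be equally consistent, provided the estimate and bounds share one scale. A table footnote could say that the percentage refers to frequency + 1.

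The cost is one sentence in the SAP and one line of programming. The model, tests, multiplicity procedure and sample size do not change.

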8.1.2.5 Subgroup analyses for the primary variables

The analyses described in Section 8.1.2.1 and 8.1.2.3 will be repeated for the subgroups described in Section 4.8. In the subgroup analyses by Baseline SV2A use, the corresponding stratification factor will be removed from the model. These evaluations will be descriptive, and the model estimates and 95% CIs will be presented.

8.1.3 Analysis of the primary efficacy variable for submission to the CFDA

Due to COVID-19 pandemic subjects (100 in total) from the China region were not enrolled

8.2 Statistical analysis of the secondary efficacy variables

Separate secondary efficacy variables have been designated for submission to US FDA/PMDA and submission to EMA.

8.2.1 Analysis of the secondary efficacy variables for submission to the US FDA, PMDA, and other regulatory authorities not referencing EMA

8.2.1.1 75% Responder Rate over the 12-week Maintenance Period

75% responder rate is the secondary efficacy variable for the US FDA and primary efficacy variable for the EMA. The analyses are described in Section 8.1.2.3.

Only subjects with > 0 seizure frequency at baseline will be included in the analysis.

8.2.1.2 50% Responder Rate over the 12-week Maintenance Period

Subjects with at least a 50% reduction in seizure frequency will be categorized as a 50% responder. The same methodology described in Section 8.1.2.3 will be used for 50% responder rate during the 12-week Maintenance Period. No multiplicity adjustment will be applied and tests will be carried out at a nominal two-sided 0.05 significance level.

Only subjects with > 0 seizure frequency at baseline will be included in the analysis.

8.2.1.3 Percent reduction from Baseline in observable focal-onset seizure frequency over the 12-week Maintenance Period

The third secondary efficacy variable is percent reduction from Baseline in observable focal-onset seizure frequency, over the 12-week Maintenance Period. The calculation of percent reduction from Baseline in seizure frequency is described in Section 8.1.1.2. The percent reduction in seizure frequency will be summarized descriptively.

Statistical comparisons between each PSL dose group and placebo will be performed on the FAS using the Wilcoxon-Mann-Whitney test. No multiplicity adjustment will be applied, and tests will be carried out at a nominal two-sided 0.05 significance level. The Hodges-Lehmann nonparametric estimator will be used to estimate the median difference between each PSL dose group versus placebo, along with the corresponding 95% CI of the estimate.

8.2.2 Analysis of the secondary efficacy variables for submission to EMA and regulatory authorities who reference EMA

8.2.2.1 The change in log-transformed observable focal onset seizure frequency from Baseline, over the 12-week Maintenance Period

The analysis described in Section 8.1.2.2 (for US FDA, PMDA, and other regulatory authorities not referencing EMA) of the change in log-transformed observable focal-onset seizure frequency from Baseline, over the 12-week Maintenance Period, serves as the key secondary variable for submission to EMA.

8.2.2.2 50% Responder Rate status over the 12-week Maintenance Period

This variable is also a secondary variable for FDA submission and is described in Section 8.2.1.2.

8.2.2.3 Percent reduction in observable focal-onset seizure frequency from Baseline, over the 12-week Maintenance Period

This variable is also a secondary variable for FDA submission and is described in Section 8.2.1.3.

8.3 Analysis of other efficacy variables

Other efficacy variables are listed in Section 2.2.1.3. These variables are the same for all regulatory agencies.

8.3.1 Derivations of other efficacy variables

For other efficacy variables based on seizure frequencies (observable focal-onset (Types IA1, IB, IC) and all Type I focal-onset seizures the frequencies), log-transformations, changes from Baseline, percent reduction from Baseline and Responder Rates during the evaluation period of interest are calculated similarly as described in Section 8.1.1, using the appropriate analysis period and responder criterion.

8.3.1.1 Seizure-freedom status (Yes/No)

A subject is defined as seizure free (ie, seizure-freedom status=Yes) during a specific evaluation period if they meet all of the following criteria:

1. The subject completed the specific time period.
2. The subject did not have any missing diary days over the time period. Missing diary day refers to no diary available at all for that day. If the diary for the day is present and 'no seizures' is checked then the diary day is not missing.
3. The subject did not report any seizure of any type over the time period.

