4.2.1.1 Missing data caused by missing seizure diary

Seizure frequency will be computed over non-missing diary days. Diary compliance evaluation is described in Section 7.2.

If seizure type is known but the number of seizures is unknown, the number of seizures will be imputed using the median for the same seizure type (daily seizure number > 0) during the same analysis period (baseline or treatment period). Otherwise, the missing seizure number will be imputed using the count of next higher level of seizure type.

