7.2 Diary compliance

Primary and secondary, and other efficacy variables are based on diary-collected seizure frequencies, and as such, diary compliance will be evaluated along with treatment compliance. Subjects are instructed to complete their diary entries at least once a day during the study. A dairy day will be considered missing for compliance if the seizure count field is checked as 'not done'. Diary compliance will be evaluated during the Baseline Period, during the entire 16-week Treatment Period, and during the Maintenance Period.

Diary compliance will be calculated as 100 times the number diary days (days with dairy completed) during the period and dividing this quantity by the expected number of diary days that should have been completed during this period of time. Compliance is only computed for actual time of participation in the study up to the end of the Treatment Period. Only data prior to and on the date of last dose of study medication will be included in the compliance calculation. If a subject didn't enter an analysis period, the diary compliance for the analysis period will not be calculated.

Diary compliance data will be listed by subject.

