8.1 Statistical analysis of the primary efficacy variables

8.1.1 Derivations of primary efficacy variables

8.1.1.1 Seizure frequency

Seizure frequency (SF) refers to the 28-day adjusted seizure frequency. The 28-day adjusted seizure frequency is defined as: $SF = (\text{Number of Seizures}) \times (28 / D)$. The number of seizures is the total number of seizures during an analysis period or time interval. For cluster seizures, the number of cluster episodes will be included. D corresponds to the number of days for which the diary was available during the analysis period or time interval.

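### Read literally, SAP 8.3.1.1 lets a completer be classed as seizure free although the seizure count on one or more diary days was 'not done'

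*SAP*

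**What the plan says.** Seizure freedom (SAP 8.3.1.1) has three criteria: the subject completed the period, has no missing diary days in it, and satisfies "The subject did not report any seizure of any type over the time period". The second criterion is explained twice. First, "Missing diary day refers to no diary available at all for that day". Second, "If the diary for the day is present and 'no seizures' is checked then the diary day is not missing". A diary that exists but carries no count is not mentioned.

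Diary compliance (SAP 7.2) uses another rule: "A dairy day will be considered missing for compliance if the seizure count field is checked as 'not done". Its scope is compliance only.

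For seizure frequency, SAP 8.1.1.1 states that "D corresponds to the number of days for which the diary was available during the analysis period or time interval", while SAP 4.2.1.1 says "Seizure frequency will be computed over non-missing diary days" and continues "Diary compliance evaluation is described in Section 7.2". SAP 3.3.1 (Baseline) and Protocol 13.6 also restrict the calculation to non-missing days.

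SAP 8.3.1.2 counts a seizure-free day only when diary data exist and show that no seizure occurred.

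Seizure freedom is analysed in SAP 8.3.2.12 on the Completer Set, by exact conditional logistic regression. SAP 8.3.2 sets a nominal two-sided 0.05 level without multiplicity adjustment.

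**The concern.** Seizure freedom is a claim about every day of the period, so each day needs positive evidence that no seizure occurred. The wording of 8.3.1.1 asks for less: a diary must exist, and no seizure may have been reported. A day on which the count was never made meets both conditions. Absence of information then passes as absence of seizures, and always in the direction of Yes.

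The numbers involved are likely to be small, which makes each classification count. Protocol 5.4.1 puts the chance of complete control with a further regimen at 1% to 4% in this kind of population. If that range carried over to a 12-week rate (an assumption), the planned 100 subjects per arm would yield 100 × 0.01 = 1 to 100 × 0.04 = 4 seizure-free subjects per arm, and fewer after early termination. With counts of that order, one misclassified subject is visible in an exact analysis.

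**Working it through.** The SAP gives no figure to reproduce here, so the check sets the rules side by side and then sizes the consequences.

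**Step 1. How each rule treats each kind of day**

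| Kind of day | 7.2 (compliance) | 8.3.1.1 (seizure freedom) | 8.1.1.1 / 4.2.1.1 (D) | 8.3.1.2 (seizure-free day) |
|---|---|---|---|---|
| No diary | no completed diary | missing | excluded | not used |
| Diary, 'no seizures' checked | completed | not missing | included | counted |
| Diary, seizure type known, number unknown | depends on the count field | a seizure is reported, so status is No | number imputed under 4.2.1.1 | not counted |
| Diary, count 'not done', no type recorded | missing | not missing as worded; no seizure reported, so it passes | not stated | not counted |

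Only the last row is in dispute. The imputation in 4.2.1.1 starts from a recorded seizure type, so it does not reach that row.

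**Step 2. Consequence for seizure freedom**

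Take a completer with 12 × 7 = 84 Maintenance days: 83 marked as having no seizures and one with the count undone. Under 8.3.1.1 as worded, status is Yes. Under the 7.2 definition, it is No. Under 8.3.1.2 the same subject has 83 seizure-free days, not 84. The percentage of seizure-free days is 83/84 = 98.8% or 83/83 = 100%, depending on whether the undone day counts as available. The subject can thus be seizure free for the whole period without every day being a seizure-free day.

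How many otherwise seizure-free completers would be affected depends on the daily probability q of an undone count, which the documents do not give. Assuming independent days, the share with a full record over 84 days is (1 − q)^84:

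- q = 0.1%: 0.919, so about 8% affected
- q = 0.5%: 0.656, so about 34% affected
- q = 1%: 0.430, so 57% affected

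**Step 3. Consequence for seizure frequency, if such days did enter D**

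With SF = seizures × 28/D (SAP 8.1.1.1) and k undone days, including them multiplies the Maintenance SF by (84 − k)/84: 0.988 for k = 1, 0.952 for k = 4 and 0.905 for k = 8. The values of k are assumptions.

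A threshold case for the 75% responder: Baseline SF 4 and 3 Maintenance seizures.

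- D = 84: SF = 3 × 28/84 = 1.000, reduction 75.00%, responder
- D = 83: SF = 3 × 28/83 = 1.012, reduction 74.70%, non-responder

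One day therefore matters only at the boundary.

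Now let the same share of days be undone in both periods: 2 of 28 at Baseline and 6 of 84 in Maintenance, with 4 and 3 seizures.

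- Days included: SF 4.000 and 1.000, reduction 75.0%
- Days excluded: 4 × 28/26 = 4.308 and 3 × 28/78 = 1.077, reduction 75.0%

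The percent reduction, and so responder status, does not change. The change in ln(SF + 1) is −0.916 against −0.938. Because of the added 1 the cancellation is not exact, but the gap is only 0.022.

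**The case against.** The strongest defence is that 7.2 and 8.3.1.1 serve different purposes and need not share a definition. The second explanatory sentence in 8.3.1.1 speaks of a diary that is present with the no-seizure box checked, which suggests that a positive entry was intended. That is a fair reading of intent. But the sentence gives a sufficient condition for a non-missing day, not a necessary one, and the sentence before it limits 'missing' to the absence of any diary. A programmer who follows the words will not exclude an undone day.

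A second defence is that the form is not in the documents. Diaries are transcribed into the eCRF (Protocol 12.2.1), and 'not done' may simply be how an absent diary is recorded. The two definitions would then describe the same day and the gap would be empty. This stands as a limit on the size of the problem; it does not repair the wording.

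A reader might go further and infer that both primary variables are biased because undone days enter D with no seizures. The documents do not say that. SAP 4.2.1.1, SAP 3.3.1 and Protocol 13.6 all limit the calculation to non-missing days, 4.2.1.1 points on to 7.2, and the 8.3.1.1 definition does not govern D. Only the reference in 8.1.1.1 to diary availability leaves the matter open. If a share m of Maintenance days were undone and counted, with a complete Baseline and seizures on those days at the usual rate, the true reduction needed to score as a 75% responder would be 1 − 0.25/(1 − m): 73.7% at m = 5%, 72.2% at 10% and 68.8% at 20%. The arithmetic is right, but those shares have no source in the documents, and the shift vanishes if Baseline is equally affected.

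Two further inferences also lack support. One is that sedated or unwell subjects leave more counts undone, so that the error differs by arm; nothing in the documents shows this, and diaries are reviewed at each visit with caregiver help allowed (Protocol 7.7 and 9.1). The other is that no output would reveal the problem: SAP Amendment 1 removed the compliance summary, but the by-subject compliance listing in 7.2 remains.

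**Conclusion.** The point holds for seizure freedom. As worded, 8.3.1.1 can class a completer as seizure free with one or more days of unknown status, and it is inconsistent with 8.3.1.2. A single such day is enough to decide the classification. The conclusion assumes that a diary can be on file while its count is marked 'not done'; the documents neither confirm nor exclude this, and they give no frequency for it.

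The reach is limited. Seizure freedom is an 'other' efficacy variable, tested without multiplicity control on completers only. For seizure frequency, and hence the two primary variables, there is an ambiguity of wording rather than a stated rule that counts the day. The text leans towards exclusion, and any effect would be small for a few days and would largely cancel if Baseline had the same share of such days.

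**What to change.** In SAP 8.3.1.1, define a diary day as non-missing only if a seizure count (including one imputed under 4.2.1.1) or an explicit no-seizure entry is recorded, and require a no-seizure entry on every day of the period for a status of Yes. Use the same definition for D in 8.1.1.1, so that it agrees with 4.2.1.1, 3.3.1 and 7.2.

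The cost is one sentence, a cross-reference and one flag in the derivation, with no new data. The downside is that some seizure-freedom classifications may change from Yes to No. The number should be small because few seizure-free completers are expected, and the by-subject diary compliance listing can be used to identify them.
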